# 4.3 Adherence Assessment

High adherence to acyclovir or placebo will be important for determining the efficacy of acyclovir in preventing HIV acquisition in this trial. The aim is to optimize and monitor adherence without excessive or unsustainable resource utilization that would make the results of this trial less generalizable in terms of implementation in developing countries.

At each monthly visit, study staff will assess participant compliance with the assigned treatment regimen through a structured interview and tablet count. Study product adherence and occurrence of genital lesions and other genital symptoms will be assessed via clinical interview and evaluation of the number of tablets

remaining in the bottles returned from their prior monthly supply of study drug. In addition, study staff will provide counseling about issues related to compliance with the study protocol, including counseling about what to do if a participant misses a dose.

## 4.4 Treatment Interruptions

Use of study drug may be interrupted if the investigator decides to withdraw the study drug temporarily due to safety concerns for the participant, in consultation with the protocol chairs, or if the participant is unable/unwilling to comply with the study procedures. If a female participant becomes pregnant during the study, she will be counseled about the available data on the safety of acyclovir during pregnancy and discontinued from further use of study drug for the duration of her participation in the study.

Whenever use of study drug is interrupted, this will be recorded on the appropriate CRF. Participants who interrupt treatment will be asked to continue to complete follow-up for endpoint determination.

# 4.5 Considerations For Women Who Become Pregnant During The Study

During the informed consent process, local site staff will discuss with female study participants the available data on acyclovir and pregnancy. Based on data from a pregnancy registry that followed 749 women with first trimester exposure to acyclovir, acyclovir use does not appear to result in an increased frequency or unusual distribution of birth defects as compared with the general population. Recent trials of daily acyclovir toward the end of pregnancy to prevent abdominal deliveries, and endorsement of such approach by the American College of Obstetricians and Gynecologists, indicate the lack of safety concerns with acyclovir. However, given limited data on safety of daily suppressive acyclovir throughout pregnancy in developing countries, women who become pregnant will discontinue use of study drug for the duration of their participation in the study; however, should the participant later have two consecutive negative pregnancy test results, she may re-start study drugs. Episodic treatment of open label acyclovir may be offered at the discretion of the clinician to women during their second and third trimesters of pregnancy. Urine pregnancy tests will be performed at quarterly visits and women will be asked about missed or late periods at monthly visits; those who report late menstrual periods will have urine pregnancy tests performed at that monthly visit. Pregnant women will be maintained in follow-up to ascertain study endpoint information. Clinical status of infants born to women who became pregnant while enrolled in the trial will be obtained by interview of the woman after delivery; if a woman exits the study prior to completion of her pregnancy, every effort will be made to obtain this information.

#### 4.6 Concomitant Medications

Only concomitant prescription medications taken in relation to a Serious Adverse Event will be recorded on applicable study case report forms.

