# 3.2 Exclusion Criteria

MSM and WSM who meet **any** of the following criteria are **not eligible** for this study:

- Known history of adverse reaction to acyclovir.
- Current or planned use of famciclovir, valacyclovir, or acyclovir (except those medications provided by study staff prior to the enrollment visit or during the study) for genital HSV (use of shortcourse antiviral therapy for herpes zoster after the enrollment visit or between screening and enrollment is allowed).
- Known plans for travel away from study site for > 2 months.

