#### **Clinical Procedures**

- Assess compliance by clinical interview and tablet count.
- Administer questionnaire to assess symptomatic STDs, including genital ulcer disease, vaginal discharge and rectal symptoms.
- Administer risk behavior & sexual history questionnaire (must take place prior to risk reduction counseling).
- Provide risk reduction counseling.
- Syndromically treat (or refer for free treatment) participant-reported symptomatic bacterial STDs.
- Provide all available test results.

For participants who report genital symptoms:

- Perform genital exam and collect swab of anogenital ulcers or other anogenital findings thought to be HSV-related, for end of study testing.
- Treat (or refer for free treatment) symptomatic bacterial STDs syndromically.

Note: For ongoing chronic conditions in the absence of new anogenital symptoms, the clinician should consult with the Protocol Chair and Co-Chair, FHI, and SCHARP to determine whether a genital examination is warranted.

For women who report missed or late menstrual period:

• Obtain urine for pregnancy test.

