#### 7.6 Data Analysis

### 7.6.1 Primary Analyses

Descriptive analyses will be carried out to determine if the randomization has resulted in treatment and control groups that are similar with respect to key baseline measures. Although treatment will be randomized by site, the distribution of other risk factors, including measures of exposure to HIV (e.g. percent time using condoms, number of partners, sexual practices) will be described by treatment group.

The primary analysis will be a survival analysis using Cox's proportional hazards model with time to detection of HIV infection as the outcome. The analysis will be based on the "intent to treat" principle and the test will be two-sided. The analysis will be stratified by risk group (MSM and heterosexual women) and a pooled relative risk will be calculated. Endpoint information will continue to be collected on women who become pregnant after randomization (although they will be discontinued from treatment during pregnancy) and these women will be included in the analysis in their original randomization group. Any other individuals who choose to discontinue study medication will be asked for permission to continue to collect endpoint information on them. Their results will also be included in the analysis in their original randomization group. Individuals who go on open label suppressive medication ("cross-overs") will be included in the original randomization group. Similarly, individuals who choose to go on open label suppressive medication will be asked to provide endpoint information and will be included in the analysis in their original randomization group. Individuals who drop out of the study and refuse further testing prior to completion of follow-up will be treated as uninformatively censored as of their last valid HIV test.

Interim monitoring for the trial is described in section 7.7.

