A proportional hazards model will be used to evaluate the effect of treatment arm on recurrence of genital ulcers. Since genital ulcers may recur multiple times over the course of follow-up, the model for recurrent events described by Anderson and Gill will be used for this analysis. Individuals will be considered to be not-at-risk for recurrences when they are being actively treated syndromically for herpes due to symptoms. The robust variance formulation described by Lin will be used to adjust the p-values and confidence intervals if multiple recurrences occur in one or more individuals. In addition, survival analysis will be performed with time to first recurrence as the dependent variable.

Through modeling, exploratory analyses will be conducted to assess the relative contribution of suppression of clinical versus subclinical

reactivation using acyclovir. To address this problem, a proportional hazards model will be fitted, with HIV seroincidence as the outcome and i) self-reported presence of genital ulcers within the past 1 month (yes/no, as well as a continuous variable), and ii) self-reported adherence to acyclovir (proportion of doses and days in which both doses were missed) as covariates. Actual use of acyclovir as opposed to randomization assignment will be used for this analysis. The (negative of the) coefficient for lesions in this model will provide a measure of the decrease in risk associated with suppression of clinical lesions. The coefficient for acyclovir will provide a measure of the protective effect of treatment after controlling for the presence of clinical lesions. Presumably, this additional protective effect is related to suppression of subclinical disease.

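### Anti-herpes drugs obtained outside the study are not recorded after enrollment, so contamination cannot be measured directly and two planned analyses in 7.6.2 lack an input they need

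*Supplement*

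**What the plan says.** Section 4.6 sets the rule for concomitant drugs: "Only concomitant prescription medications taken in relation to a Serious Adverse Event will be recorded on applicable study case report forms". Under 6.2, adverse event collection is itself confined to SAEs, so this opening is narrow.

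Other sections presuppose knowledge of non-study anti-herpes drugs:

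- Section 3.2 excludes people with "Current or planned use of famciclovir, valacyclovir, or acyclovir" for genital HSV, with exceptions for study-supplied drug and short-course zoster treatment.
- Section 7.6.1 expects some participants to move to open-label suppression. It calls them cross-overs, keeps them in their randomized group, and says "individuals who choose to go on open label suppressive medication will be asked to provide endpoint information".
- Section 7.6.2 has an exploratory model for HIV infection in which "Actual use of acyclovir as opposed to randomization assignment will be used for this analysis". The measure it names is "self-reported adherence to acyclovir (proportion of doses and days in which both doses were missed) as covariates".
- Section 7.6.2 also takes participants out of the risk set for ulcer recurrence while they are under active treatment for herpes symptoms.

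What the plan does collect concerns study-supplied product. The monthly instruction in 5.4 is "Assess compliance by clinical interview and tablet count". Section 4.4 adds "Whenever use of study drug is interrupted, this will be recorded on the appropriate CRF". Section 4.2 requires pharmacy dispensing records.

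**The concern.** The protocol anticipates off-study suppression but, as written, gives sites nowhere to record it. Its own text makes such use conceivable. Participants are told that they are HSV-2 positive and what the trial is testing, 1.2 describes generic acyclovir as inexpensive, and 7.5 accepts that some placebo recipients with recurring lesions may suspect their assignment.

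The trial is presented as a proof of concept that uses acyclovir as a probe of HSV-2 suppression. If the relative risk comes out near 1, the first question will be whether the arms really differed in suppression. Part of the answer is how much placebo person-time was spent on outside drug, and that quantity would be unknown to the analysts and to the DSMB. It cannot be recovered reliably afterwards.

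**Working it through.** **1. Is there any capture outside 4.6?** The sources that might supply it:

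| Source | What it covers | Non-study anti-HSV drug? |
|---|---|---|
| 4.6 | Prescription drugs related to an SAE | Only if SAE-related |
| 4.3, 5.4 | Interview and tablet count for assigned product | No |
| 4.4 | Interruption of study drug | Shows that tablets stopped, not what replaced them; misses anyone taking both |
| 4.2 | Pharmacy records | Study-supplied drug only |
| 5.5, 5.6 | Exam, symptom and risk questionnaires, blood | Not named |
| Appendix I | Medical history at enrollment, quarterly and exit visits | Content unspecified |

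No passage provides for it. Detailed procedures and CRFs are deferred to the SSP manual and the SDMC (5, 10.2), and neither is shown.

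**2. Which analyses need it?**

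- *Primary Cox model (7.6.1).* Participants are analyzed as randomized "and the test will be two-sided". Cross-overs need not be identified for the test or the estimate.
- *Actual-use model (7.6.2).* The covariate is adherence to study product. A placebo participant on outside acyclovir is coded unexposed, and an acyclovir participant who replaces study tablets with outside drug is coded non-adherent.
- *Ulcer recurrence model (7.6.2).* Time under treatment obtained elsewhere remains in the at-risk denominator, because its dates are unknown.

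**3. Reproduce the design figure.** Inputs from 7.3: two-sided alpha 0.05, power 90%, r = 0.51.

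L = {(1.960 + 1.282) / (0.5 × ln 0.51)}² = 92.7, rounded up to 93, as stated. Power at 93 events = Φ(0.5 × √93 × 0.673 − 1.96) = 0.901.

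**4. Illustrate contamination.** Assumption, not in the documents: a fraction c of placebo person-time carries the active-arm hazard. Then

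RR = 0.51 / (1 − 0.49c), and power = Φ(0.5 × √93 × |ln RR| − 1.96).

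| c | RR | Power at 93 events | Events for 90% power |
|---|---|---|---|
| 0 | 0.510 | 90.1% | 93 |
| 5% | 0.523 | 87.8% | 100 |
| 10% | 0.536 | 85.2% | 109 |
| 20% | 0.565 | 78.5% | 130 |

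For scale, 7.3 moved the design value from about 0.5 to 0.51 to allow for stopping drug in pregnancy. It makes no stated allowance for cross-over. A c of about 4% produces a shift of the same size: 0.51 / (1 − 0.49 × 0.04) = 0.520.

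These losses come from contamination itself. They arise whether or not anyone records it.

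**The case against.** Much of the case on the other side stands.

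- **The primary result does not depend on this record.** Correct. A reader might infer that the primary analysis is compromised because cross-overs cannot be identified. The documents do not support that: 7.6.1 keeps them where they were randomized.
- **Actual use is measurable for study drug.** Correct. Adherence, interruption and dispensing data cover what the study supplies. Only the non-study part is missing, and the model concerned is exploratory.
- **A null result would not be uninterpretable.** Also fair. Ulcer occurrence and frequency are compared by arm as a secondary endpoint, and lesions are swabbed for HSV PCR, with testing during the study allowed by Letter of Amendment #7. Heavy placebo-arm suppression should shrink that difference. The check is indirect, however: a small ulcer difference could also reflect poor adherence, and outside treatment disturbs the ulcer analysis itself.
- **Outside use may be rare.** Possibly. Current or planned use for genital HSV is excluded, study-supplied episodic treatment is offered (extended to oral sores by Letter of Amendment #5), and 8.5.2 and 8.8 treat wider access to acyclovir as still to be secured. The documents give no rate either way.
- **The unseen SSP manual or CRFs may hold such an item.** They may, so it cannot be said that use is never captured. But 10.4 requires full compliance with the protocol, and such an item would conflict with the restrictive wording of 4.6.

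A reader might also infer that the exclusion in 3.2 should be widened beyond genital HSV. Nothing in the documents shows that this would matter.

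**Conclusion.** The gap is real but limited. As written, the protocol provides no recording of non-study systemic anti-HSV drugs after enrollment unless an SAE is involved. The validity of the intention-to-treat analysis is unaffected. What is lost is a direct measure of placebo-arm contamination, correct exposure coding in one exploratory model, and complete not-at-risk time in the ulcer recurrence analysis of a secondary endpoint.

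The relative risks and power figures above rest entirely on assumed values of c and on full suppression during contaminated time. They show what contamination would do, not what the missing record costs, and a reader should not take them as power that better recording would restore. The conclusion also assumes that the SSP manual and CRFs, which are not shown, follow 4.6. On this footing the point is a worthwhile, inexpensive improvement to the plan and not a threat to its main result.

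**What to change.** Amend 4.6 so that systemic acyclovir, valacyclovir and famciclovir are exempt from the SAE-only limit. At each monthly, quarterly and exit visit, record any use not supplied as blinded study drug: drug, start and stop dates, reason and source.

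Then state in the analysis sections that this log, together with the dispensing records for study-supplied open-label courses, defines cross-overs in 7.6.1 and both actual use and not-at-risk time in 7.6.2. Report it by arm to the DSMB alongside compliance (7.7).

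The cost is one short question and a log entry at visits that already take place, plus the wording changes. The primary analysis and the sample size do not change.

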## 5 STUDY PROCEDURES

An overview of the study visit and procedures schedule is presented in Appendix I. Presented below is additional detail on visit-specific study procedures. Detailed instructions to guide and standardize all study procedures across sites will be provided in the study-specific procedures manual.

#### 5.1 Screening Visit 1 (up to Day -60)

Written informed consent for screening will be obtained before any screening procedures are initiated. Eligibility for the study will be determined over the course of the Screening Visits and Enrollment Visit, based on HIV and HSV-2 testing and the inclusion/ exclusion criteria in sections 3.1 and 3.2. Participants at sites without rapid HIV testing will be told when they can return for their HIV test results. As noted in Section 3.4, for participants who do not meet the study eligibility criteria, the screening process will be discontinued when ineligibility is determined.

#### Administrative, Behavioral, And Regulatory Procedures

- Obtain informed consent for screening.
- Collect demographic information.
- Obtain locator information.
- Administer behavioral eligibility checklist.
- Provide condoms.
- Schedule next visit.

#### **Clinical Procedures**

- Provide HIV and HSV-2 pre-test and risk reduction counseling.
- Collect blood.
- Provide all available test results and post-test counseling.

For female volunteers:

• Collect urine sample.

#### Laboratory Procedures

- HIV serology.
- HSV-2 serology.

For female volunteers:

• Urine pregnancy test.

#### 5.2 Screening Visit 2 (between Day –60 and Enrollment)

#### Administrative, Behavioral, And Regulatory Procedures

- Provide information about the study.
- Update locator information.
- Provide condoms.
- Provide all available test results.
- Schedule next visit (unless the participant is enrolled during this visit).
- Obtain a second blood sample (only if repeat testing of HIV or HSV-2 is necessary).

#### **Clinical Procedures**

• Provide HIV and HSV-2 test results and post-test counseling.

#### 5.3 Enrollment Visit - Baseline (Day 0)

Written informed consent for study participation will be obtained before any "onstudy" procedures are initiated. For participants whose eligibility is not confirmed at this visit, the screening and enrollment process will be concluded when ineligibility is determined. If a screened volunteer returns more than 60 days after screening, he or she must repeat all screening procedures and a second enrollment visit will need to be scheduled.

#### Administrative, Behavioral, And Regulatory Procedures

- Obtain informed consent for study participation.
- Obtain random assignment.
- Update locator information.
- Obtain informed consent for storage of blood for future testing (optional)
- Provide condoms.
- Schedule next visit.

#### **Clinical Procedures**

- Obtain medical history.
- Administer risk behavior & sexual history questionnaire (must take place prior to risk reduction counseling).
- Administer questionnaire to assess symptomatic STDs, including genital ulcer disease, vaginal discharge and rectal symptoms.
- Administer questionnaire to assess 3-month history of symptomatic STDs, such as genital ulcer disease, vaginal discharge and rectal symptoms.
- Provide risk reduction counseling.
- Perform genital exam for signs of STDs.

• Collect specimens for STD baseline assessment:

```
> MSM:
⇒ Rectal swab
⇒ urine
> WSM:
⇒ cervical and vaginal swabs
⇒ urine
```

- Collect blood.
- Provide all available test results.
- Treat bacterial STDs, if clinically indicated, or refer for free treatment.
- Supply study drug, instructions, and adherence counseling.

#### Laboratory Procedures

- STD testing as follows:
  - > MSM:
    - $\Rightarrow$  rectal gonorrhea culture.
    - ⇒ urine LE; if > trace or urethritis symptoms: gonorrhea / chlamydia rapid, or NAAT, or urethral culture

> WSM:

- ⇒ cervical swabs for gonorrhea and chlamydia (culture, or rapid, or NAAT)
- $\Rightarrow$  vaginal pH, wet mount for clue cells, whiff test and T. vaginalis
- $\Rightarrow$  gram stain (to be sent forbatched reading at the end of the study), and
- $\Rightarrow$  trichomonas In-pouchTM local
- $\Rightarrow$  urine pregnancy test (with a sensitivity of 50 mIU/ml hCG).
- Storage of blood for confirmatory WB for HSV-2 antibodies at the University of Washington.
- Syphilis serology (including titer if initial test is reactive). Confirm with a treponemal specific test if initial test is reactive.
- Storage of genital lesions swabs at -20°C for later evaluation of etiology of genital ulcers and any other genital findings thought to be HSV-related by PCR testing at UW.
- Storage of left-over sera for CL and on-site specimen archive (to be tested for HIV, in the case of positive result on the first postenrollment HIV test, and/or creatinine in the event of renal insufficiency).

The sites will have a chain of custody that will provide for the storage conditions of the samples. Each sample type will have a different processing and storage condition depending on the internal procedures the site uses.

#### 5.4 Follow-Up Visits: Monthly (Months 1 To 12 or 18)

The following activities will take place **each month**:

#### Administrative, Behavioral, And Regulatory Procedures

- Update locator information.
- Provide study drug for following month and adherence counseling.
- Provide condoms.
- Schedule next visit.

#### **Clinical Procedures**

- Assess compliance by clinical interview and tablet count.
- Administer questionnaire to assess symptomatic STDs, including genital ulcer disease, vaginal discharge and rectal symptoms.
- Administer risk behavior & sexual history questionnaire (must take place prior to risk reduction counseling).
- Provide risk reduction counseling.
- Syndromically treat (or refer for free treatment) participant-reported symptomatic bacterial STDs.
- Provide all available test results.

For participants who report genital symptoms:

- Perform genital exam and collect swab of anogenital ulcers or other anogenital findings thought to be HSV-related, for end of study testing.
- Treat (or refer for free treatment) symptomatic bacterial STDs syndromically.

Note: For ongoing chronic conditions in the absence of new anogenital symptoms, the clinician should consult with the Protocol Chair and Co-Chair, FHI, and SCHARP to determine whether a genital examination is warranted.

For women who report missed or late menstrual period:

• Obtain urine for pregnancy test.

#### Laboratory Procedures

For swabs from participants with genital ulcers or other possible HSV-related anogenital findings:

• Storage of swabs for end of study testing to determine etiology by PCR at UW.

For women who report missed or late menstrual period:

• Urine pregnancy test.

Site staff should make every effort to have participants report to the clinic for study visits (Monthly, Quarterly, Interim, or Exit). Participants may be unable to report to the clinic for a study visit for a variety of reasons. Should the participant be willing, site staff will conduct the appropriate visit off-site (not in the clinic), attempting to perform all protocol-required visit procedures while maintaining participant confidentiality. If a participant refuses any protocol-specified procedures, this should be appropriately documented in the clinic/chart notes. An approved off-site/ remote visit SOP must be in place prior to conducting off-site visits, and site staff may conduct no more than 3 such consecutive visits

Determining that an off-site visit is necessary will be done only after all other options for scheduling the visit have been explored (e.g., earlier or later office hours, interim visits). All scheduling efforts will be documented in the participant's chart notes and/or contact logs. The actual off-site visit may take place within the visit window or after the window is closed; if it occurs outside of any study window it is considered an interim visit (see the Study Specific Procedures Manual for interim visit procedures and for more detailed approval steps for such a visit).

In-person contact with participants is the preferred method of collecting study data. However, there may be rare circumstances in which telephone contact may be the only method available for collecting data.

Telephone data collection is permitted only when ALL of the following conditions have been met:

- 1. a participant is unable to travel to the study site (e.g., due to physical incapacitation, being out of state)
- 2. conducting an in-person visit prior to the next regular visit is impractical
- 3. the visit to be conducted is a monthly visit (Screening, Enrollment, Quarterly, and Exit Visits NOT allowed)
- 4. site staff can verify the participant's correct identity
- 5. the participant's confidentiality is protected

Determining that a telephone visit is necessary will be done only after all other options for scheduling the visit have been explored (e.g., earlier or later office hours, interim visits, off-site visits). All scheduling efforts will be documented in the participant's chart notes and/or contact logs. The actual phone visit may take place within the visit window or after the window is closed; if it occurs outside of any study window it is considered an interim visit (see the Study Specific Procedures Manual for interim visit procedures and for more detailed approval steps for such a visit).

